### 3. Purpose and rules of this statistical analysis plan

#### 3.1. Purpose of preparation of this statistical analysis plan

The purpose of this statistical analysis plan is to determine the matters related to statistical analysis activities conducted in accordance with the implementation plan of the “Special Drug Use-Results Survey (All-Case Surveillance) on Humira® (generic name: adalimumab [genetical recombination])” (hereafter referred to as “this survey”). This is one of the surveys conducted in compliance with the GPSP Ordinance, and partial or total results of the analysis will serve as data used for reporting of the special drug use-results survey on Humira to authorities and preparation of application materials for reexamination.

## 4. Survey summary

### 4.1. Purpose of the survey

This survey is conducted as the special drug use-results survey on Humira® Subcutaneous Injection (generic name: adalimumab [genetical recombination]) for the purpose of understanding the following matters in all patients with juvenile idiopathic arthritis with active articulation treated with Humira.

- 1) Unknown adverse reactions (clinically significant adverse reactions in particular)
- 2) Incidence of adverse reactions under actual use conditions
- 3) Factors considered to have an influence on safety, efficacy, etc.

### 4.2. Survey plan

The survey objects are all patients with juvenile idiopathic arthritis with active articulation who have a poor response to existing treatment and are to receive Humira. All patients who are to receive Humira will be enrolled after this indication is approved, and aggregation, analysis, and reporting to authorities will be conducted when data from 100 patients have been collected. Even after regulatory reporting, enrollment of patients will be continued until the final evaluation is obtained from regulatory authorities.

### 4.3. Planned sample size

100 patients

## 5. Items to be assessed in analysis and examining method

### 5.1. Safety

#### 5.1.1. Occurrence of adverse reactions

For adverse reactions, see “Data derivation and calculation methods”.

Diagrams will be created to examine the incidence rates of adverse reactions.

#### 5.1.2. Occurrence of serious adverse events

For serious adverse events, see “Data derivation and calculation methods”.

Diagrams will be created to examine the incidence rates of serious adverse events.

### 5.2. Efficacy

#### 5.2.1. Presence or absence of efficacy

For setting of efficacy, see “Data derivation and calculation methods”.

Diagrams will be created to examine the remission rates.

### 5.2.2. Trends in efficacy endpoints

For setting of efficacy, see “Data derivation and calculation methods”.

Diagrams will be created to compare the values before the start of treatment, at 4, 8, 12, 16 and 24 weeks of treatment.

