## ② Use of other drugs

Presence/absence of concomitant drug use for conditions other than JIA, names of drugs, routes, doses, and durations

If an adverse event occurs: Names of drugs, reasons for use, routes, doses, and durations

- 6) Non-drug concomitant therapy
  - Non-drug concomitant therapy for JIA
- 7) Presence/absence of tuberculosis or serious respiratory diseases
  - Date of confirmation, method of diagnostic imaging, and presence/absence and type of abnormal findings
- 8) Clinical evaluation
  - Patients will be evaluated for the following at the time points described below:
    - ① DAS28 (number of tender joints and number of swollen joints), global assessment by patient (VAS), global health by physician (VAS), erythrocyte sedimentation rate (ESR, 1 hr value), and CRP. (Baseline, and Weeks 4, 8, 16, and 24 weeks of treatment)
    - ② Serum MMP-3 level. (Baseline, and Weeks 4, 8, 16, and 24 weeks of treatment)
    - ③ Anti-CCP antibody (Baseline and 24 weeks of treatment)
    - ④ Height and body weight. (Baseline, and Weeks 4, 8, 16, and 24 weeks of treatment)
- 9) Discontinuation of Humira treatment
  - Reasons for discontinuation of Humira treatment
  - Treatment after discontinuation of Humira treatment
- 10) Adverse events (including abnormal laboratory findings)
  - Presence/absence of adverse events, nature of adverse events, dates of onset, seriousness, causal relationship with Humira treatment, suspected drugs, clinical course of adverse events, measures taken (measures related to Humira treatment and symptomatic treatment), outcomes, and laboratory findings (indicate laboratory values when abnormal laboratory findings are observed).
- 11) Items of investigation of particular interest
  - Occurrence of infections, tuberculosis, malignant tumor, administration site reactions, autoimmune diseases, pancytopenia, demyelinating disease, congestive heart failure, and interstitial pneumonia.

(4) Preparation of written consent form for transition to self-injection and self-injection transition record

It will be confirmed whether written consent for transition to self-injection has been obtained and a self-injection transition record has been prepared.

(5) Presence/absence of malignant tumor during the long-term follow-up period.

Patients will be evaluated for the occurrence of malignancy during the first and second years of treatment.

(6) Product Quality Complaints

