#### 9.13. Test methods

In this analysis plan, a paired t-test should be conducted for the amount of change from before the start of administration. For the incidence rates and remission rates (DAS28) of adverse reactions for each background factor, Fisher's exact test or Mann-Whitney U test should be conducted. Tests should not include an unknown/unspecified category.

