## 12. Handling of data on tests/timing of assessment

Timing and period category	Handling of data
Time window for efficacy assessment	Before the start of treatment: from the start date of Humira treatment - 30 days to the start date of Humira treatment At Week 4 of treatment: from the start date of Humira treatment + 1 day to the start date of Humira treatment + 42 days At Week 8 of treatment: from the start date of Humira treatment + 43

Timing and period category	Handling of data
	
days to the start date of Humira treatment + 70 days
 
At Week 12 of treatment: from the start date of Humira treatment + 71 days to the start date of Humira treatment + 98 days
 
At Week 16 of treatment: from the start date of Humira treatment + 99 days to the start date of Humira treatment + 140 days
 
At Week 24 of treatment: from the start date of Humira treatment + 141 days to the start date of Humira treatment + 196 days
 
At the final assessment: the data measured at the end during the period from the start date of Humira treatment + 1 day to the start date of Humira treatment + 196 days.

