Purpose of analysis: For DAS28-4/ESR, the number of patients, the number of patients remitted and the remission rate will be calculated on the basis of combination therapy for juvenile idiopathic arthritis (no, yes, unknown/unspecified). For patients receiving combination therapy, the number of patients, the number of patients remitted and the remission rate by breakdown of combination therapy (rehabilitation, other, unknown) will be calculated.

Notes: The breakdown of combination therapy may be redundantly aggregated.

“Table 3.2.3 Remission rates by duration of combination use of MTX for juvenile idiopathic arthritis”

Analysis object: Patients included in the efficacy analysis set

Purpose of analysis: For DAS28-4/ESR, the number of patients remitted and the remission rate will be calculated on the basis of combination use of MTX for juvenile idiopathic arthritis (no, yes, unknown/unspecified). Where there is a duration of combination use of MTX, the number of patients, the number of patients remitted and the remission rate by breakdown of duration of combination use (after the start of Humira treatment up to the end date of Humira treatment, at least a dose used during Humira treatment, unknown/unspecified) will be calculated.

Notes: The breakdown of duration of combination use may be redundantly aggregated.

“Table 3.3 Changes in anti-CCP antibodies”

Analysis object: Patients included in the efficacy analysis set

Purpose of analysis: For anti-CCP antibodies, the basic statistics of values measured before the start

of treatment and at 24 weeks after the start of treatment will be calculated in accordance with “12. Handling of data on tests/timing of assessment” (time window for efficacy assessment). Basic statistics will also be calculated for the amount of change from before the start of treatment, and a paired t-test will be conducted.

Note: None in particular.

“Table 3.4.1 Changes in DAS 28-4/ESR”

Analysis object: Patients included in the efficacy analysis set (DAS28-4/ESR)

Purpose of analysis: For DAS28-4/ESR, the basic statistics of values measured before the start of treatment, at 4, 8, 12, 16 and 24 weeks after the start of treatment, and at the final assessment will be calculated in accordance with “12. Handling of data on tests/timing of assessment” (time window for efficacy assessment). Basic statistics will also be calculated for the amount of change from before the start of treatment, and a paired t-test will be conducted.

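### The SAP windows, reports and tests a Week 12 efficacy time point that the protocol does not schedule; check the case report form and reconcile the two documents

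*SAP*

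**What the plan says.** **Protocol.** In section 8(3), under clinical evaluation, the DAS28 components, both VAS scores, ESR, CRP, MMP-3, height and weight carry the schedule "Baseline, and Weeks 4, 8, 16, and 24 weeks of treatment". Section 9(1), on efficacy items to be analysed, repeats it. Anti-CCP antibody is taken at baseline and Week 24 only. Week 12 appears in neither list.

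**SAP.**
- Section 5.2.2 compares pre-treatment values with values "at 4, 8, 12, 16 and 24 weeks of treatment".
- Section 12 gives Week 12 the window "from the start date of Humira treatment + 71 days to the start date of Humira treatment + 98 days". Week 8 ends just before it, at +70 days, and Week 16 runs "from the start date of Humira treatment + 99 days to the start date of Humira treatment + 140 days".
- Section 13.3 reports Week 12 in Tables 3.4.1, 3.4.2, 3.5.1, 3.5.3, 3.6.1, 3.6.2 and 3.7 and in Figures 3.5.3.1 to 3.5.3.5. Table 3.4.1 is typical: statistics for values before treatment and "at 4, 8, 12, 16 and 24 weeks after the start of treatment, and at the final assessment will be calculated".
- Section 9.13 states that "a paired t-test should be conducted for the amount of change from before the start of administration". Tables 3.4.1, 3.4.2, 3.6.1, 3.6.2 and 3.7 each repeat this.
- Section 9.1 rules out imputation in the analysis, apart from defined completion of some input items.

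The SAP gives no reason for adding Week 12.

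**The concern.** The documents disagree about which visits exist, and the disagreement changes how data are assigned. A window for a visit that nobody schedules still collects values: late Week 8 visits, early Week 16 visits, and unscheduled or discontinuation assessments that fall between +71 and +98 days.

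On the protocol's schedule, the patients in the Week 12 column would be there because of the timing of their visits. The column would nevertheless stand beside the scheduled visits in the trend tables and bar graphs, with its own p-values. Because nothing is imputed, each displaced value would also be missing from Week 8 or Week 16.

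**Working it through.** **Inputs.** SAP section 12 windows, in days after the start of treatment: Week 4 = +1 to +42, Week 8 = +43 to +70, Week 12 = +71 to +98, Week 16 = +99 to +140, Week 24 = +141 to +196. Nominal days are 7 × week: 28, 56, 84, 112 and 168.

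**1. Reproduce the SAP's cut-points.** Take the midpoint of neighbouring nominal days, with Week 12 included:
- (28 + 56)/2 = 42
- (56 + 84)/2 = 70
- (84 + 112)/2 = 98
- (112 + 168)/2 = 140

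All four match, so the windows follow a midpoint pattern on a schedule that includes Week 12.

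**2. Apply the same pattern to the protocol's schedule** (28, 56, 112, 168):
- (28 + 56)/2 = 42
- (56 + 112)/2 = 84
- (112 + 168)/2 = 140

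Week 8 becomes +43 to +84 and Week 16 becomes +85 to +140. The Week 12 window is 98 − 71 + 1 = 28 days wide. Of these, 14 (+71 to +84) would belong to Week 8 and 14 (+85 to +98) to Week 16.

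**3. Which scheduled visits are relabelled Week 12?**
- Week 8: 71 − 56 = 15 to 98 − 56 = 42 days late.
- Week 16: 112 − 98 = 14 to 112 − 71 = 41 days early.

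Smaller deviations stay in their own window.

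**4. Tests at Week 12.** DAS28-ESR, DAS28-CRP, CDAI and SDAI give one each. Table 3.7 adds nine: tender joints, swollen joints, patient VAS, physician VAS, ESR, CRP, MMP-3, height and weight. Total 4 + 9 = 13.

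**5. How many records might move?** The documents give no data on visit timing. As an assumption, let actual visit days be normal around the nominal day with standard deviation s, and let all 100 patients attend. With half-day continuity limits, the expected number of Week 12 records per 100 patients is

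100 × {[Φ(42.5/s) − Φ(14.5/s)] + [Φ(−13.5/s) − Φ(−41.5/s)]}.

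| s (days) | late Week 8 | early Week 16 | records per 100 patients |
|---|---|---|---|
| 5 | 0.0019 | 0.0035 | 0.5 |
| 7 | 0.0192 | 0.0269 | 4.6 |
| 10 | 0.0735 | 0.0885 | 16.2 |
| 14 | 0.149 | 0.1659 | 31.5 |

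The result depends almost wholly on s, so the table shows a range and is not a forecast. It leaves out unscheduled assessments.

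**The case against.** **The CRF may have a Week 12 field.** It is a protocol attachment and was not available. The SAP takes visit data from the clinical-course section of the CRF, and version 1.0 is dated October 2017, after registration closed in February 2016, so its authors may have known of a Week 12 entry. This stands: a reader might infer that Week 12 certainly holds only off-schedule values, and the documents do not establish that. Against it, the protocol was last amended on 6 April 2018, after SAP version 2.0 of 28 March 2018, and its sections 8 and 9 still have no Week 12. One document needs correcting in either case.

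**Not every efficacy output is touched.** This stands. Table 3.3 (anti-CCP) uses baseline and Week 24 only, and Table 3.5.2 uses the final assessment only.

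**Rates at Week 12.** A reader might infer that Week 12 remission and response rates will look falsely low, since SAP section 9.10 makes the analysis set the default denominator and Tables 3.5.1 and 3.5.3 name no other. That goes further than the documents allow. The rule would act on any visit with missing values, section 9.10 permits a different denominator if footnoted, and no expected Week 12 count is given. It is a separate question from the schedule.

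**Labelling by nearest week is defensible, and new windows have a cost.** In part this stands. A value at day 80 is closer to Week 12 than to Week 8. The SAP's section 12 has no rule for choosing among several values in one by-visit window, and widening Week 8 from 28 to 42 days makes such duplicates more likely. In the tables of means the number of patients is reported, so a sparse Week 12 would be visible there. None of this explains why an unscheduled visit should be presented and tested as a time point.

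**Conclusion.** The inconsistency is certain: both protocol lists omit Week 12, and the SAP includes it in section 5.2.2, in its windows and in the seven tables and five figures named above. The consequence is conditional. If the CRF follows the protocol, the Week 12 column and its 13 paired t-tests rest on displaced or unscheduled values, and Weeks 8 and 16 lose visits at least 15 days late or 14 days early. The number lost cannot be derived from the documents; about 0.5 to 32 records per 100 patients is what the assumed timing spreads of 5 to 14 days give.

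The reach is limited to the by-visit efficacy outputs. Final-assessment results do not depend on the Week 12 label, because that value is the last one between +1 and +196 days. Tables 3.3 and 3.5.2, the safety analyses and the 100-patient target are also unaffected. The point should be corrected because the results feed reexamination reporting, but it does not threaten the survey's main safety purpose.

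**What to change.** Check the CRF first.

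- **If it has no Week 12 visit:** delete Week 12 from SAP section 5.2.2, section 12, Tables 3.4.1, 3.4.2, 3.5.1, 3.5.3, 3.6.1, 3.6.2 and 3.7, and Figures 3.5.3.1 to 3.5.3.5. Set Week 8 to +43 to +84 days and Week 16 to +85 to +140 days, following the SAP's own midpoint pattern. Where a window holds several values, use the one nearest the nominal day. Record the change from any output already produced.
- **If it does collect Week 12:** keep the windows and correct protocol sections 8 and 9.
- **In either case:** show the number of patients assessed at each visit in every by-visit table and figure.

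Cost: changes of wording and, in the first case, re-windowing of data already held. The drawback there is some loss of comparability with the analysis planned for around December 2017. If that analysis was run, the new windows would be set after results had been seen, and the report should say so.

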## 6. Implementation status and schedule of analyses

Purpose of analysis	Implementation status (survey unit period, if implemented)	Timing to prepare analysis results
Reexamination replacement	From July 1, 2011 to August 4, 2017	Around December 2017
Final report	From July 1, 2011 to around June 2018	Around June 2018

## 7. Software/dictionaries used for analysis

### 7.1. Statistical analysis and tabulation software

Software and versions used for analyses are shown below.

	Software and version
OS	Microsoft Windows 7 or later
Statistical analysis software	SAS Ver. 9.2 or later
Tabulation software	Microsoft Excel 2007 or later

### 7.2. Dictionaries used

Dictionaries used for adverse event terms, complication terms and drug names are shown below.

Item	Dictionary name and version	Remarks
Type of adverse event and adverse reaction/infection	ICH Medical Dictionary for Regulatory Activities/Japanese version (MedDRA/J) *An appropriate version is used for aggregation according to the timing of analysis.	

Adverse events and adverse reactions are classified into System Organ Class (SOC), and appropriate terms should be selected from Preferred Terms (PT).

When SOC is indicated, it should be in accordance with the order of international agreements.

When PT is indicated, it should be in accordance with the order

Item	Dictionary name and version	Remarks
		
of MedDRA/J code.
 
 
The version of the MedDRA/J used should be clarified in the margin.
 

Drug name (concomitant drug)	Prescription drug data file *An appropriate version should be used for aggregation according to the timing of analysis.	
 
In principle, 7-digit codes should be used for aggregation of concomitant drugs by drug.
 
In a list of concomitant drugs (including Appended Form 3 for Reexamination), LLT codes should be preferentially used (including Appended Form 3 for Reexamination).
 

## 8. Definition of populations used for analysis

Name of population	Definition
Enrolled patients	Patients determined to be eligible for enrollment.
Patients with fixed CRFs	Enrolled patients whose CRF was fixed.
Patients with no CRF collected	Of the enrolled patients, those who have no CRF collected.
Patients excluded from the safety analysis set	
Of the patients with fixed CRFs, those who meet any of the following from the list of inclusion of patients.
 
 
Breach of contract
 
Unsigned facility/clinical department
 
Excess of contracted patients
 
Humira not administered
 
Humira not administered (revealed after collection of a CRF)
 
Humira administered before contract
 
The start date of Humira treatment is outside of the contracted period (survey period)
 
Registration criteria violation/ineligible patient
 
Patients not eligible for the survey (revealed after collection of a CRF)
 
Not confirmed by a doctor
 
Patients whose CRF was signed by a person other than the contracting doctor
 
Unenrolled patient
 
Patients who have not been enrolled but whose CRF has been collected
 
Duplicate patient
 

Name of population	Definition
	
Patients enrolled redundantly within the survey
 
 
Patients transferred to another hospital
 
Duplicate patient within the survey due to hospital transfer
 
Patients with withdrawn consent
 
Patients who withdrew consent to participation in the survey/study or to the use of data
 
Patients ineligible for safety assessment
 
No record of safety assessment (it is unknown whether or not the patient had any adverse event)
 
Data reliability not confirmed (medical facility closed down or merged, doctor transferred to another facility, confirmation refused by doctor, inconsistent content of CRF)
 
Reliability of the data cannot be confirmed, and an entrustor gave instructions separately
 

Patients included in the safety analysis set	Patients with fixed CRFs excluding patients excluded from the safety analysis set
Patients excluded from the efficacy analysis set	
Of the patients included in the safety analysis set, those who meet any of the following from the list of inclusion of patients.
 
 
Disease not eligible to the survey
 
Disease defined as not eligible to the survey in the implementation plan
 
Patient ineligible for efficacy assessment
 
DAS 28 (4/ESR) cannot be calculated at any time points after administration of Humira
 

Patients included in the efficacy analysis set	Patients included in the safety analysis set excluding patients excluded from the efficacy analysis set.

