##### “Figure 1.2 Breakdown of patients included in the safety analysis set”

Analysis object: Patients included in the efficacy analysis set

Purpose of analysis: For patients included in the safety analysis set, number of patients included in the efficacy analysis set (DAS28-4CRP), number of patients who cannot be assessed with DAS28-4CRP, number of patients included in the efficacy analysis set (CDAI), number of patients who cannot be assessed with CDAI, number of patients included in the efficacy analysis set (SDAI), number of patients who cannot be assessed with SDAI, number of patients included in the efficacy analysis set (DAS28-4/ESR), and number of patients who cannot be assessed with DAS28-4/ESR will be calculated for each efficacy endpoint.

Note: This table will be output on a separate sheet as an appendix to Figure 1.1 Patient composition diagram when the aggregate results in Figure 1.1 is output.

“Table 1.1 Aggregate results of discontinuation of treatment”

Analysis object: Patients included in the safety analysis set

Purpose of analysis: For patients who discontinued treatment and the breakdown of the reasons for discontinuation (remission, subtherapeutic response, onset of adverse events, patient's request, no hospital visit [including hospital transfer], other), the number and percentage of patients will be calculated.

Notes: • The breakdown of the reasons for discontinuation may be redundantly aggregated.

- The denominator of the percentage of patients who discontinued treatment should be patients included in the safety analysis set, and the denominator of the percentage in the breakdown of the reasons for discontinuation should be patients who discontinued treatment as defined in “10.1 General”.
- “Onset of an adverse event” should apply only when “Onset of an adverse event” is selected and an adverse event during safety analysis period has occurred.

“Table 1.2 Aggregate results of switching to other biological products”

Analysis object: Patients included in the safety analysis set

Purpose of analysis: For the number of patients switched to other biological products and the breakdown of the reasons for switching (remission, subtherapeutic response, onset of adverse events, patient's request, no hospital visit [including hospital transfer], other), the number and percentage of patients will be calculated.

Notes: • The breakdown of the reasons for switching may be redundantly aggregated.

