Note: None in particular.

“Table 3.4.2 Changes in DAS28-4/CRP”

Analysis object: Efficacy analysis set (DAS28-4/CRP)

Purpose of analysis: For DAS28-4/CRP, the basic statistics of values measured before the start of treatment, at 4, 8, 12, 16 and 24 weeks after the start of treatment, and at the final assessment will be calculated in accordance with “12. Handling of data on tests/timing of assessment” (time window for efficacy assessment). Basic statistics will also be calculated for the amount of change from before the start of treatment, and a paired t-test will be conducted.

Note: None in particular.

“Table 3.5.1 Changes in EULAR response”

Analysis object: Patients included in the efficacy analysis set (DAS28-4/ESR)

Purpose of analysis: For improvement in DAS28-4/ESR assessed by EULAR Response Criteria, the number and percentage of patients will be calculated on the basis of improvement in DAS28-4/ESR at 4, 8, 12, 16 and 24 weeks after the start of treatment and at the final assessment in accordance with “12. Handling of data on tests/timing of assessment” (time window for efficacy assessment). Furthermore, the number of patients showing efficacy and the efficacy rate of improvement in DAS28-4/ESR as well as its 95% confidence interval will be calculated.

Note: None in particular.

“Table 3.5.2 Efficacy rates assessed by EULAR Response Criteria by background factor”

Analysis object: Patients included in the efficacy analysis set (DAS28-4/ESR)

Purpose of analysis: For improvement in DAS28-4/ESR assessed by EULAR Response Criteria at

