Analysis object: Patients included in the efficacy analysis set

Purpose of analysis: For tender joint count, swollen joint count, VAS assessed by the patient, VAS assessed by a doctor, ESR, CRP, serum MMP-3 concentration, height and weight, the basic statistics of values measured before the start of treatment, at 4, 8, 12, 16 and 24 weeks after the start of treatment, and at the final assessment will be calculated in accordance with “12. Handling of data on tests/timing of assessment” (time window for efficacy assessment). Basic statistics will also be calculated for the amount of change from before the start of treatment, and a paired t-test will be conducted.

Note: None in particular.

“Table 4.1 List of patients excluded from the safety analysis set and patients excluded from the efficacy analysis set of special drug use-results surveys, etc. (including reasons for exclusion)”

Analysis object: Patients excluded from the safety analysis set, patients excluded from the efficacy analysis set

Purpose of analysis: A list of case numbers for patients excluded from the safety analysis set and patients excluded from the efficacy analysis set, and patients for whom the reason for exclusion was output will be created.

Note: Where one patient has more than one reason for exclusion, they should be linked with commas when output.

“Table 4.2 List of patients”

Analysis object: Patients with fixed CRFs

Purpose of analysis: A list of patients analyzed will be created for the following items:

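### One efficacy set gated on post-dose DAS28-4/ESR discards observed non-ESR data in Tables 3.3 and 3.7, and the endpoint-specific sets for DAS28-4/CRP, CDAI and SDAI are undefined, with conflicting parents in Figure 1.2

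*SAP*

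**What the plan says.** SAP section 8 gives one definition of the efficacy set: "Patients included in the safety analysis set excluding patients excluded from the efficacy analysis set". There are two grounds for exclusion. One is a disease outside the survey; the other is that "DAS 28 (4/ESR) cannot be calculated at any time points after administration of Humira". No endpoint-specific efficacy set is defined there.

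SAP section 13 then names several sets. Table 3.4.2 reads "Analysis object: Efficacy analysis set (DAS28-4/CRP", and Tables 3.6.1 and 3.6.2 carry the labels CDAI and SDAI in the same way. Tables 3.3 and 3.7 name the efficacy set without a qualifier. Table 3.3 covers anti-CCP. Table 3.7 begins "For tender joint count, swollen joint count, VAS assessed by the patient, VAS assessed by a doctor, ESR, CRP, serum MMP-3 concentration" and goes on to height and weight.

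Figure 1.2 is the only place that shows where the labelled sets come from. It is titled "Figure 1.2 Breakdown of patients included in the safety analysis set", but its next line is "Analysis object: Patients included in the efficacy analysis set". Its text starts "For patients included in the safety analysis set, number of patients included in the efficacy analysis set (DAS28-4CRP" and ends with the "number of patients who cannot be assessed with DAS28-4/ESR will be calculated for each efficacy endpoint".

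**The concern.** There are two separate problems.

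First, a criterion that belongs to one score decides who appears in tables of other variables. A patient with CRP, MMP-3 or anti-CCP measured before and after the start of treatment drops out of Tables 3.3 and 3.7 if DAS28-4/ESR was never calculable after dosing. The protocol (section 9, efficacy information) lists these items in their own right and does not make them conditional on DAS28-4/ESR.

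Second, the parent population of the DAS28-4/CRP, CDAI and SDAI sets is not settled. Two programmers working from the same SAP could produce different denominators for Tables 3.4.2, 3.6.1 and 3.6.2, in results meant for the authority (SAP section 3.1).

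**Working it through.** **The plan's own figure.** The only sample-size figure is 100 patients, chosen to detect an ADR of 3% incidence with 95% probability (protocol section 2). The check is 1 − 0.97^100 = 0.952, so it reproduces. It concerns safety and this point does not affect it.

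**Step 1: which outputs need ESR.** The formulas are in SAP sections 9.5 to 9.7.

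| Output | Needs ESR? | Set named | Defined in section 8? |
|---|---|---|---|
| 3.3 anti-CCP | No | efficacy set, unqualified | Yes, gated on DAS28-4/ESR |
| 3.7 joint counts, both VAS, CRP, MMP-3, height, weight | No (only its ESR row) | efficacy set, unqualified | Yes, gated on DAS28-4/ESR |
| 3.4.2 DAS28-4/CRP | No | labelled DAS28-4/CRP | No |
| 3.6.1 CDAI | No | labelled CDAI | No |
| 3.6.2 SDAI | No | labelled SDAI | No |

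**Step 2: who fails the criterion.** DAS28-4/ESR = 0.56√(tender) + 0.28√(swollen) + 0.70 ln(ESR) + 0.014 × (patient VAS). Section 9.1 does not impute, so a visit with any component missing gives no score. On the natural reading of section 8, exclusion needs this to happen at every post-dose time point. Section 12 gives five post-dose windows from +1 to +196 days, so one missing ESR excludes nobody. Two groups can fail:

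- No usable ESR at any post-dose visit, other components present. DAS28-4/CRP can be scored if CRP is present, CDAI if the doctor's VAS is present, and SDAI if both are.
- Joint counts or patient VAS missing throughout. All four scores are then incalculable, so Tables 3.4.2, 3.6.1 and 3.6.2 lose nothing. Any CRP, MMP-3, anti-CCP, height and weight values are still lost from Tables 3.3 and 3.7.

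**Step 3: the parent of the labelled sets.** The two readings of Figure 1.2 compare as follows.

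- *Efficacy set as parent* (its analysis-object line). Patients in the first group cannot enter Tables 3.4.2, 3.6.1 or 3.6.2. The figure's count of patients not assessable by DAS28-4/ESR would be zero by construction.
- *Safety set as parent* (its title and text, and the fact that it counts DAS28-4/ESR non-assessable patients at all). The first group is kept. The ineligible-disease exclusion, however, is part of the efficacy-set definition and is not restated for these sets. The note to Table 3.5.3 shows that efficacy-set membership is what removes persistent oligoarthritis. As written, such patients could enter Tables 3.4.2, 3.6.1 and 3.6.2.

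The loss in Tables 3.3 and 3.7 is the same under either reading.

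**Step 4: size, by assumption only.** Let m be the share of safety-set patients who have no calculable post-dose DAS28-4/ESR but do have the endpoint in question. The documents do not give m. Take 100 safety-set patients, also an assumption, since registration continues beyond the first 100. The number left is 100(1 − m) and the standard error inflation is 1/√(1 − m) − 1. If the excluded patients' mean change differs from that of the retained patients by 0.5 SD (a further assumption), the estimate shifts by 0.5m SD. The standard error in SD units is 1/√(100(1 − m)).

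| m | Patients left | SE inflation | Shift (SD) | SE (SD) |
|---|---|---|---|---|
| 5% | 95 | 2.6% | 0.025 | 0.103 |
| 10% | 90 | 5.4% | 0.05 | 0.105 |
| 20% | 80 | 11.8% | 0.10 | 0.112 |
| 30% | 70 | 19.5% | 0.15 | 0.120 |

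**The case against.** The best defence is that DAS28-4/ESR is the SAP's main efficacy measure (remission, EULAR response). Showing supportive variables in one common evaluable population keeps Table 3.7 aligned with Table 3.4.1, and the protocol speaks of a single count of patients evaluable for efficacy. This would carry weight if the SAP kept to one population. It does not: it already names separate sets for the sister scores, so the common-population principle cannot explain why Tables 3.3 and 3.7 alone stay behind the DAS28-4/ESR gate.

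Other parts of the defence stand. Figure 1.2's title, its text and its DAS28-4/ESR non-assessable count all favour the safety set as parent. A reader might infer that patients without ESR are definitely dropped from Tables 3.4.2, 3.6.1 and 3.6.2. The documents do not support that, because it follows only from the figure's analysis-object line, which the rest of the figure contradicts.

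A reader might also infer that any missing ESR or VAS removes a patient, or that the tables are shown to be biased. Neither follows. Exclusion needs failure at every post-dose time point, and nothing in the documents says how often that happens or how such patients differ. The protocol (section 6(3)) also has discontinued patients followed to week 24, and a patient with no later visit would lack the other endpoints too.

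**Conclusion.** The point holds in two parts. Following the SAP as written, Tables 3.3 and 3.7 discard observed values on endpoints that do not need ESR, for every patient with no calculable post-dose DAS28-4/ESR. The sets used in Tables 3.4.2, 3.6.1 and 3.6.2 are undefined in section 8 and have contradictory parents in Figure 1.2; patients without any usable ESR may be dropped from those scores, but this is not established.

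The size cannot be computed from the documents and may be small. Over an assumed 5% to 30% affected, standard errors in Tables 3.3 and 3.7 would rise by 2.6% to 19.5%. The shift in mean change rests on a further assumed 0.5 SD difference and is illustration only. The conflict between definitions does not depend on any of these assumptions. These are secondary descriptive tables, so the change is worth making but does not touch the safety objective.

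**What to change.** In SAP section 8:

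- Apply the DAS28-4/ESR criterion only to the DAS28-4/ESR outputs (3.1, 3.2.x, 3.4.1, 3.5.x), and reword it as calculable at no post-dose time point, if that is what is meant.
- Define the sets for Tables 3.4.2, 3.6.1, 3.6.2 and 3.3, and for each variable in Table 3.7, as safety-set patients with an eligible disease and at least one post-start value of that endpoint.
- For change statistics and paired t-tests, also require a baseline value of that endpoint, so that the stated set size is the number analysed.

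In SAP section 13, correct Figure 1.2's analysis object to the safety set, and state which efficacy set Table 1.3 describes.

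The cost is SAP wording and one filter per table. Denominators will differ between tables and need footnotes. SAP section 9.10 already asks for the set and its size to be stated, and for a footnote where a percentage uses another denominator.
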